## **12.1.** Determination of Sample Size

In Part 1 of the study, a cohort of 6 subjects will receive open-label APL-9 (as add-on therapy to SOC), and safety data will be evaluated to determine initiation of Part 2. No formal sample size calculation was performed.

In Part 2 of the study, with approximately 30 subjects treated in each treatment group, there is a greater than 95% chance of an SAE being reported if the true incidence is 10% or higher. Similarly, there is a 26%, 71%, or 89% chance of an SAE being reported if the true incidence is 1%, 4%, or 7%, respectively.

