3. STUDY DESIGN

3.1 Overview of Study Design

This is a randomized, double-blind, vehicle-controlled, multicenter, parallel-group Phase 1/2 study (with an initial open-label period) evaluating the safety and efficacy of APL-9 versus those of vehicle as an add-on therapy to standard of care in subjects who have respiratory failure (including mild to moderate ARDS) due to COVID-19 infection.

The study will be conducted in 2 parts:

Part 1 (Open-Label Period):

Initially, a cohort of 6 subjects will receive open-label treatment with APL-9 as add-on therapy to standard of care from Day 1 through Day 7 or resolution of ARDS (PaO2/FiO2 ratio >300 mm Hg), whichever occurs earlier. Resolution of ARDS in this study is defined according to the Berlin definition as PaO2/FiO2 ratio >300 mm Hg (ARDS Definition Task Force 2012).

An independent data monitoring committee (DMC) will review the clinical data available for all 6 subjects once the last subject in Part 1 reaches Day 7 or is discharged following the resolution of ARDS (PaO2/FiO2 ratio >300 mm Hg). The DMC will recommend to the sponsor whether:

- the study can proceed to Part 2, and
- the maximum allowed treatment duration in Part 2 can be extended. (The DMC can extend the treatment duration beyond Day 7 up to and including Day 21; refer to Part 2 [Randomized Double-Blind Period]).

Follow-up safety assessments for each subject will be collected 30 days following the last dose of APL-9 (with a +7-day window). These assessments will be conducted via inpatient assessment (for patients still hospitalized) or by telephone call (for patients discharged).

Part 2 (Randomized Double-Blind Period):

Part 2 of the study will only be initiated upon recommendation from the DMC. Required criteria for initiation of Part 2 will include 1) No fatal/life-threatening SAEs thought possibly related to APL-9 by the DMC, and 2) no more than 1 subject requiring premature treatment discontinuation by the investigator due to AEs or abnormal lab tests. All subjects will receive standard of care independent of their randomization. Approximately 60 subjects will be randomly assigned at a 1:1 ratio to blinded treatment with either APL-9 or saline vehicle. Subjects will receive treatment with APL-9 or vehicle from Day 1 through Day 7, discontinuation of respiratory support (supplemental oxygen or mechanical ventilation), or hospital discharge, whichever occurs latest.

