3.3 Randomization (Part 2 Only)

In Part 2, approximately 60 subjects will be randomly assigned to receive either APL-9 plus standard of care or vehicle control plus standard of care at 1:1 ratio. Randomization will be stratified by need of mechanical ventilation (yes vs no) and age (younger than 65 years vs at least 65 years).

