5.2 Demographics and Baseline Characteristics

Demographics and baseline characteristics will be summarized for safety set including:

- Age at screening (years)
 If not collected, then it will be calculated as (year of informed consent form signed birth year)
- Age in categories (<65 years and ≥ 65 years)
- Sex, Childbearing Potential, Race, Ethnicity
- Baseline Weight (kg), Height (cm), Body Mass Index (BMI, kg/m²)
- Randomization Stratification Factors (Part 2 Only)
- Baseline use of mechanical ventilation, Baseline use of supplemental oxygen
- Baseline Respiratory Rate, Oxygen Saturations, Temperature, Blood Pressure (Systolic and Diastolic), Heart Rate
- Baseline Level of Consciousness
- Baseline Sequential Organ Failure Assessment (SOFA) score

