6. EFFICACY ANALYSIS

All efficacy analyses will be summarized for each study part. Efficacy data will also be analyzed by treatment group in Part 2. Hypothesis testing will be performed for part 2 between two treatment groups.

Unless otherwise specified, baseline for all efficacy analyses is defined as the last non-missing measurement recorded prior to taking the first dose of study drug.

All CIs will be presented as 2-sided 90% and/or 95% CIs. All statistical tests will be 2-sided hypothesis tests performed at the 10% level of significance.

The primary efficacy analyses will be performed for full analysis set (FAS). The supportive efficacy analyses will be performed for Intent-to-Treat (ITT) set.

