The p-values will be from a 2-sided unstratified Log-rank test and stratified Log-rank test by the randomization stratification factors [need of mechanical ventilation (yes vs no) and age (younger than 65 years vs at least 65 years)] at 0.1 significant level for evaluation of treatment difference. These time-to-event endpoints will be summarized via Kaplan-Meier (KM) methodology using the 25th, 50th (median), and 75th percentiles and pre-specified timepoints, each with associated 2-sided 90% confidence intervals. Point estimate of hazard ratio will be obtained from a Cox regression model with treatment and the randomization stratification factors as fixed factors and the 90% CI will be obtained using Wald method.

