6.2.2 Sequential Organ Failure Assessment (SOFA) score

Organ failure status will be assessed using the SOFA score (see Table 1), which assesses 6 organ systems: respiration, coagulation, liver, cardiovascular, central nervous system, and renal (Ferreira et al., 2001). A subject will be defined as being free of organ failure when the SOFA score is zero. The SOFA score will be assessed at baseline on Day 1 and as listed in the schedule of assessment (SOA), based on worst daily values. SOFA score at each assessment and changes from baseline over time will be summarized using descriptive statistics.

Table 1: Sequential Organ Failure Assessment (SOFA) Scoring

Variables	0	1	2	3	4	
Respiration						
PaO ₂ /FiO ₂ , mmHg	>400	≤400	≤300	≤200ª	≤100a	
or SpO ₂ /FiO ₂ , mmHg	≥512	≥357 to <512	≥214 to <357	≥89 to <214	<89	
Coagulation						
$Platelets \times 10^3/\mu L$	>150	≤150	≤100	≤50	≤20	
Liver						
Bilirubin, mg/dL ^b <1.2		1.2 -1.9	2.0 -5.9	6.0 -11.9	>12.0	
Cardiovascular						

Hypotension	No hypotension	MAP <70 mm Hg	Dopamine ≤5 or dobutamine (any dose) ^c	Dopamine >5, epinephrine ≤0.1, or norepinephrine ≤0.1°	Dopamine >15, epinephrine >0.1, or norepinephrine >0.1 ^c	
Central nervous system						
Glasgow Coma Scale score ^{d,e}	15	13 -14	10 -12	6 -9	<6	
Renal						
Creatinine, mg/dL or urine output (mL/d) ^f	<1.2	1.2 to 1.9	2.0 to 3.4	3.5 to 4.9 or <500	>5.0 or <200	

Abbreviations: FiO2 = fraction of inspired oxygen; MAP = mean arterial pressure.

- 5 Seems able to talk
- 3 Questionable ability to talk
- 1 Generally unresponsive

Source: Ferreira et al. 2001.

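### The Cox models for hospital stay and oxygen duration could also adjust for pre-dose baseline SOFA, which the trial already collects; the gain depends on how prognostic it is beyond ventilation and age

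*SAP*

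**What the plan says.** SAP section 6.2.1 obtains the hazard ratio for each time-to-event endpoint from a "Cox regression model with treatment and the randomization stratification factors as fixed factors", with a 90% Wald interval. SAP section 3.3 names the factors: "Randomization will be stratified by need of mechanical ventilation (yes vs no) and age (younger than 65 years vs at least 65 years").

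The hypothesis tests are separate from that model: "The p-values will be from a 2-sided unstratified Log-rank test and stratified Log-rank test by the randomization stratification factors". On the level, SAP section 6 says: "All statistical tests will be 2-sided hypothesis tests performed at the 10% level of significance".

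SOFA is collected. SAP section 6.2.2 states: "The SOFA score will be assessed at baseline on Day 1". Section 5.2 lists "Baseline Sequential Organ Failure Assessment (SOFA) score" among the baseline characteristics to be tabulated, and section 6.2.2 plans descriptive summaries of SOFA over time. No model uses it.

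The endpoints concerned are secondary, and both documents mark the primary efficacy analysis as not applicable. On size, SAP section 3.1 says: "Approximately 60 subjects will be randomly assigned at a 1:1 ratio". Protocol section 12.1 justifies this only by the chance of seeing a serious adverse event: "there is a 26%, 71%, or 89% chance of an SAE being reported if the true incidence is 1%, 4%, or 7%, respectively". Neither document states an effect size, event count or power for the time-to-event endpoints.

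**The concern.** Two binary factors describe severity coarsely here. Inclusion criterion 3 (protocol section 8.1) runs from supplemental oxygen to invasive ventilation. Exclusion criterion 7 (section 8.2) removes only subjects with kidney and liver failure together, so a subject with one of them can enter. Five of the six SOFA organ systems are non-respiratory, and neither stratification factor captures them.

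If SOFA predicts time to discharge or time on oxygen beyond ventilation and age, a Cox model without it has two costs. A non-null hazard ratio lies nearer 1 than the one conditional on SOFA, and power falls, even with perfect balance. A chance difference in severity between two arms of about 30 also stays in the estimate. For discharge and coming off oxygen, most subjects can be expected to have the event, so one more continuous term is affordable.

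**Working it through.** **1. The plan's own figure.** The chance of at least one serious adverse event among 30 subjects is 1 − (1 − p)^30. For p = 1%, 4%, 7% and 10% this gives 26.0%, 70.6%, 88.7% and 95.8%. The stated 26%, 71%, 89% and more than 95% are correct. They say nothing about the time-to-event endpoints.

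**2. Rough power without covariates.** Schoenfeld's formula is power ≈ Φ(√d/2 × |ln HR| − 1.645). With d = 50 events (assumed):
- HR 2.0: 3.536 × 0.693 − 1.645 = 0.806, power 79%.
- HR 1.5: 3.536 × 0.405 − 1.645 = −0.21, power 42%.

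**3. Simulated effect of adding SOFA.**
- From the documents: about 60 subjects, 1:1, the two strata, two-sided 10% level, follow-up to Day 51.
- Assumed: 25% ventilated, 40% aged 65 or over, exponential discharge times, discharge hazard ratios of 0.5 (ventilation) and 0.7 (age), and the treatment and SOFA effects in the table.
- The SOFA hazard ratio per SD is for the part of the score not explained by ventilation and age.
- Wald tests at 10%; 4,000 trials per row; no deaths; about 55 to 59 discharges.

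| True HR | SOFA HR per SD | Median HR, without → with SOFA | Cox power, without → with SOFA | Stratified log-rank power |
|---|---|---|---|---|
| 2.0 | 1.0 | 2.058 → 2.078 | 82.7% → 82.1% | 78.9% |
| 2.0 | 0.85 | 2.038 → 2.087 | 81.7% → 82.4% | 78.5% |
| 2.0 | 0.7 | 1.944 → 2.063 | 76.6% → 81.3% | 72.3% |
| 2.0 | 0.5 | 1.727 → 2.044 | 62.8% → 79.6% | 59.1% |
| 1.5 | 1.0 | 1.535 → 1.545 | 46.8% → 46.7% | 43.1% |
| 1.5 | 0.85 | 1.517 → 1.540 | 45.1% → 46.8% | 41.0% |
| 1.5 | 0.7 | 1.465 → 1.522 | 40.5% → 44.6% | 37.5% |
| 1.5 | 0.5 | 1.405 → 1.539 | 34.8% → 45.7% | 32.1% |

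The gains are 0.7 and 1.7 points at 0.85, 4.7 and 4.1 at 0.7, and 16.8 and 10.9 at 0.5. If SOFA adds nothing (1.0), nothing material changes. The planned log-rank test loses power in the same way as SOFA becomes more prognostic.

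**4. With deaths.** SAP section 6.2.1 imputes the longest observed stay for subjects who die. Assumed here: a 15% base death rate, deaths likelier with worse SOFA and unaffected by treatment, and imputed stays carrying no discharge event. Over 2,500 trials per setting at a true HR of 2.0, Cox power without → with SOFA is:
- SOFA HR per SD 0.85: 36.8% → 38.3%, a gain of 1.5 points.
- 0.7: 34.8% → 37.2%, about 2 points.
- 0.5: 31.2% → 41.4%, about 10 points.

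**5. No treatment effect.** Without deaths, the median hazard ratio is 0.99 to 1.01 in both models, so there is no pull. Wald rejection is 11% to 12% in both. With deaths it is about 11% without SOFA and 11% to 13% with it, the highest (13.1% against 11.1%) where SOFA is strongest. The stratified log-rank test stays at 9.6% to 11.3%. Monte Carlo error is about 1 point.

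**6. Chance imbalance.** With 30 per arm, the between-arm difference in mean SOFA, in SD units, has standard deviation √(2/30) = 0.26. A gap above 0.25 SD has probability 2 × (1 − Φ(0.25/0.258)) = 33%. To first order, such a gap shifts the treatment log hazard ratio by 0.25 × |ln(HR per SD)|: 0.04, 0.09 and 0.17 at 0.85, 0.7 and 0.5, or factors of about 1.04, 1.09 and 1.19.

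**The case against.** Four points on the other side carry weight.

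- **The planned tests are log-rank.** The Cox model supplies only the estimate and interval. A reader might infer that adding SOFA to the Cox model raises the power of the planned tests. It does not; those p-values stay as they are. This stands, and an adjusted test has to be pre-specified if the power gain is wanted.
- **Attenuation is not bias.** A reader might infer that the planned hazard ratios are wrong. The strata-adjusted and SOFA-adjusted hazard ratios are different quantities (non-collapsibility), and at a true value of 1 they coincide. Adjusting for the stratification factors matches the randomization and is valid. This stands.
- **The loss is conditional.** The documents give no prognostic strength for SOFA, and it overlaps with ventilation: the two worst respiratory scores are defined with respiratory support. The simulation allows for this by varying only the part of SOFA beyond the strata, but which row applies is unknown. A reader might infer an established loss; the documents do not support one.
- **The Day 1 score may not be purely pre-dose.** SOFA uses the worst values of the day (SAP section 6.2.2). SAP section 12.3 defines baseline as before or on first administration, whereas SAP section 6 requires a value before the first dose. Adjusting for a score that contains post-dose values could itself bias the estimate. This stands as a condition on the fix.

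The endpoints are also secondary in a Phase 1/2 safety trial. That limits the importance of the point, but it does not remove the benefit of using a covariate already in hand.

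**Conclusion.** The point holds as an efficiency improvement, not as the correction of an error. The model in SAP section 6.2.1 is valid, but it leaves out a severity score that the trial already collects. For hospital stay and oxygen duration, adding that score is close to neutral at worst and useful if it is prognostic beyond ventilation and age.

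Without deaths the gain runs from about nil to 17 points of power. With 15% deaths held at the longest stay it is smaller, up to about 10 points at a true hazard ratio of 2.0. In the strongest of those settings the adjusted Wald test also rejects about 2 points more often under no effect, so the 10 points somewhat overstate the real gain. All sizes rest on the assumed SOFA effect, treatment effect, stratum mix and death rate. Only the sample size, allocation, strata, test level and follow-up come from the documents.

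**What to change.** Before database lock, amend SAP section 6.2.1 as follows.

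- Add baseline SOFA total score, continuous, as a covariate in the Cox models for hospital length of stay and total duration of oxygen therapy.
- Define the covariate from strictly pre-dose values, and state that this overrides the worst-of-day rule and the wording of SAP section 12.3.
- Give a simple rule for missing components or a missing total, such as the overall median.
- Report the SOFA-adjusted Wald or score test at the two-sided 10% level beside the planned log-rank tests. The score form is the more cautious choice, since the log-rank (score) tests stayed nearer 10% in the simulation.
- Keep the strata-only model for overall survival. At the assumed 15% there would be 0.15 × 60 = 9 deaths, too few for four terms. Leave mechanical ventilation duration as planned too: it includes only subjects ventilated at the start, about 0.25 × 60 = 15 at the assumed 25%.

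The cost is SAP wording, one more model term, a missing-score rule and a hazard ratio that must be described as conditional on SOFA. No new data collection is needed if the pre-dose components can be identified in the recorded data.

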6.2.2 Sequential Organ Failure Assessment (SOFA) score

Organ failure status will be assessed using the SOFA score (see Table 1), which assesses 6 organ systems: respiration, coagulation, liver, cardiovascular, central nervous system, and renal (Ferreira et al., 2001). A subject will be defined as being free of organ failure when the SOFA score is zero. The SOFA score will be assessed at baseline on Day 1 and as listed in the schedule of assessment (SOA), based on worst daily values. SOFA score at each assessment and changes from baseline over time will be summarized using descriptive statistics.

Table 1: Sequential Organ Failure Assessment (SOFA) Scoring

Variables	0	1	2	3	4	
Respiration						
PaO ₂ /FiO ₂ , mmHg	>400	≤400	≤300	≤200ª	≤100a	
or SpO ₂ /FiO ₂ , mmHg	≥512	≥357 to <512	≥214 to <357	≥89 to <214	<89	
Coagulation						
$Platelets \times 10^3/\mu L$	>150	≤150	≤100	≤50	≤20	
Liver						
Bilirubin, mg/dL ^b <1.2		1.2 -1.9	2.0 -5.9	6.0 -11.9	>12.0	
Cardiovascular						

Hypotension	No hypotension	MAP <70 mm Hg	Dopamine ≤5 or dobutamine (any dose) ^c	Dopamine >5, epinephrine ≤0.1, or norepinephrine ≤0.1°	Dopamine >15, epinephrine >0.1, or norepinephrine >0.1 ^c	
Central nervous system						
Glasgow Coma Scale score ^{d,e}	15	13 -14	10 -12	6 -9	<6	
Renal						
Creatinine, mg/dL or urine output (mL/d) ^f	<1.2	1.2 to 1.9	2.0 to 3.4	3.5 to 4.9 or <500	>5.0 or <200	

Abbreviations: FiO2 = fraction of inspired oxygen; MAP = mean arterial pressure.

- 5 Seems able to talk
- 3 Questionable ability to talk
- 1 Generally unresponsive

Source: Ferreira et al. 2001.

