- b Fully eligible subjects can have screening assessments on the same day as baseline, which is defined as the day of initial study drug treatment.
- c Confirmation of SARS-CoV-2 infection may be completed more than 7 days before baseline. Presence of SARS-CoV-2 viral RNA or viral antigen may be detected in respiratory specimens (collected using nasopharyngeal or oropharyngeal swabs) with a qualitative nucleic acid amplification test (such as reverse transcriptase polymerase chain reaction), viral antigen test, or other diagnostic method that is authorized, cleared, or approved by the US Food and Drug Administration or equivalent authority for SARS-CoV-2 viral detection. Note: Serology-based antibody tests do not detect presence of virus and therefore are not considered diagnostic for active infection and cannot be used for study eligibility screening or for subsequent SARS-CoV-2 assessments.
- d Height/weight can be by subject assertion.
- e Discharged subjects who are followed up by phone will be provided with emergency study cards that include a list of symptoms associated with infections. The study card also guides subjects with instructions to contact their study physicians or seek emergency medical care if they experience any of the listed symptoms.
- f For continuous variables, the worst observed daily value will be recorded. Vital signs and ECG must be collected between the administration of the loading dose of study treatment and the initiation of the maintenance dose.
- g SOFA score variables (PaO2/FiO2 ratio or SpO2/FiO2 ratio, platelets, bilirubin, hypotension/vasopressor use, GCS score, creatinine) are detailed in Section 11.1.1 and Appendix 1.
- h A list of laboratory assessments is provided in Section 11.1.8. Blood will be collected 3 times on Day 1: (1) once prior to administration of the APL-9 bolus, (2) once as soon as possible following the bolus (within 5-10 minutes) prior to the continuous infusion, and (3) once at 2 hours after the beginning of the continuous infusion. Following that, assessments should be collected within the time frame of each calendar day. The use of silica reagents in coagulation panels should be avoided in subjects treated with APL-9.

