## 11. STUDY ASSESSMENTS AND PROCEDURES

- Day 1 is defined as the day upon which study treatment is first administered.
- The last predose assessments will be considered as baseline assessments.
- Study procedures and their timings are summarized in the SoA (Table 1). Protocol waivers or exemptions are not allowed.
- Significant safety concerns should be discussed with the sponsor immediately upon occurrence or awareness to determine whether the subject should continue or discontinue study participation.
- Adherence to the study design requirements, including those specified in the SoA (Table 1), is essential and required for study conduct.
- All screening evaluations must be completed and reviewed to confirm that potential subjects meet all eligibility criteria. The investigator will maintain a screening log to record details of all subjects screened and to confirm eligibility or record reasons for screening failure, as applicable.
- Procedures conducted as part of the subject's routine clinical management and obtained before signing of the informed consent form (ICF) may be utilized for screening or baseline purposes provided that the procedures met the protocol-specified criteria and were performed within the time frame defined in the SoA (Table 1).
- The study end-of-treatment assessments are to be conducted at the end of treatment or on the day of hospital discharge, whichever occurs later. The posttreatment follow-up assessment, conducted 30 days after the last dose of study drug (with a +7-day window), may be conducted either in the hospital or by telephone so that subjects do not have to be exposed to the hospital environment after hospital discharge.
- Discharged subjects will be provided with emergency study cards that include a list of symptoms associated with infections. The study card also guides subjects with instructions to contact their study physicians or seek emergency medical care in the event they experience any of the listed symptoms.

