#### 11.1.1. SOFA Score

Organ failure status will be assessed using the SOFA score, which assesses 6 organ systems: respiration, coagulation, liver, cardiovascular, central nervous system, and renal (Ferreira et al. 2001). A subject will be defined as being free of organ failure when the SOFA score is zero. The score will be assessed at baseline on Day 1 and as listed in the SoA based on worst daily values.

The SOFA score variables to be assessed are:

- PaO2/FiO2 ratio (mm Hg) or SpO2/FiO2 ratio—collected and entered into the database locally (see calculation instructions in Appendix 1)
- Platelets  $\times 10^3/\mu$ L—based on data provided by the local laboratory
- Bilirubin ( $\mu$ mol/L or mg/dL)—based on data provided by the local laboratory
- Hypotension/use of vasopressors—collected and entered into the database locally
- Glasgow Coma Scale score—collected and entered into the database locally (see Appendix 2)
- Creatinine (µmol/L or mg/dL)—based on data provided by the local laboratory

See Appendix 1 for additional information on calculating the SOFA score.

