12.3 Definition of Baseline

Unless otherwise stated, baseline is defined as the last non-missing measurement prior to or on the first administration of study drug (Study Day 1). Baseline can be on the same date as the first dose, given the measurement is expected prior to first dose when only date information is available. If there are repeated measurements with more than one evaluable result for the visit which could not be distinguished by time, mean value will be defined as baseline.

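### Baseline SOFA is scored on the dosing day from worst daily values with no predose cut-off, which conflicts with the predose baseline set elsewhere in both documents

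*SAP*

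**What the plan says.** Change in SOFA score is a secondary objective (protocol 6.1.2, SAP 2.1.2). The scoring rule in SAP 6.2.2 is "The SOFA score will be assessed at baseline on Day 1 and as listed in the schedule of assessment (SOA), based on worst daily values". Protocol 11.1.1 has "The score will be assessed at baseline on Day 1 and as listed in the SoA based on worst daily values", and Appendix 1 repeats it. None of these adds a predose limit. SAP 6.2.2 then summarises the score at each assessment and its change from baseline with descriptive statistics.

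Protocol 11 fixes the day: "Day 1 is defined as the day upon which study treatment is first administered". It also sets a general baseline rule: "The last predose assessments will be considered as baseline assessments". Protocol 12.3 agrees for efficacy, and protocol 12.4 takes the last predose value for laboratory tests and vital signs. SAP 6, leaving room for stated exceptions, has this default: "baseline for all efficacy analyses is defined as the last non-missing measurement recorded prior to taking the first dose of study drug".

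SAP 12.3 adds a rule for records that carry a date but no clock time: "Baseline can be on the same date as the first dose, given the measurement is expected prior to first dose when only date information".

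**The concern.** Day 1 holds both predose and post-dose hours. A worst value taken over that day can come from after the loading dose, so a baseline built from it can be partly a post-treatment measurement. If a subject deteriorates after dosing and recovers by Day 3, the deterioration raises baseline and the recovery counts as improvement. An early benefit could likewise be partly hidden, because the baseline would already contain some treated hours.

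The predose rule in protocol 11 and SAP 6 would remove this, but it brings another problem. It takes the last single predose measurement, while later visits are scored from the worst of the day. One reading set against a daily worst tends to show worsening when nothing has changed.

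So one rule gives windows of similar length but lets treated hours into baseline. The other gives a clean baseline but unequal windows. The plan does not say which applies.

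**Working it through.** **The plan's own figures.** The documents give no SOFA mean, SD or Day 1 event rate. The only sample-size figures (protocol 12.1, SAP 3.2) are chances of seeing at least one SAE among 30 subjects. The formula 1 − (1 − p)^30 gives 95.8%, 26.0%, 70.6% and 88.7% at p = 10%, 1%, 4% and 7%, which agrees with the plan. None of these depends on SOFA.

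**Step 1. What falls after dosing on Day 1.**
- Laboratory items (platelets, bilirubin, creatinine): Table 1 footnote h says "Blood will be collected 3 times on Day 1". One draw is before the bolus, one 5-10 minutes after it, and one 2 hours into the continuous infusion. Two of the three are post-dose.
- Blood pressure: Table 1 footnote f requires a vital-sign collection between the loading and maintenance infusions and asks for the worst daily value of continuous variables. The recorded Day 1 value can therefore be post-dose.
- Vasopressor use, oxygenation and coma score: no clock time or cut-off is given.

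**Step 2. Whether another rule settles it.**
- The predose rules in protocol 12.3 and SAP 6 apply unless something else is specified, and SAP 6.2.2 is the more specific text. It does not say whether it is an exception.
- The date-only rule in SAP 12.3 asks whether a measurement is expected before dosing. A worst-of-day composite has no single time, and Table 1 places it in the combined screening/baseline column (Day −7 to 1). The rule neither clearly admits it nor excludes it.

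**Step 3. Literal reading, one illustrative record.** Predose SOFA is 4 with a cardiovascular score of 0. After the loading dose the subject receives a vasopressor for at least 1 hour, as the SOFA table requires, at a level scoring 3. It is off by Day 3, when SOFA is 4.
- Change from the predose score: 4 − 4 = 0.
- Change under the literal rule: 4 − (4 + 3) = −3, an apparent 3-point improvement.

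**Step 4. Effect on the arm comparison.** Let f be the excess proportion of APL-9 over vehicle subjects with a transient post-dose rise, and d the points gained. The difference in mean change moves by −f × d, toward APL-9. Both inputs are assumed:

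| f | d | shift |
|---|---|---|
| 0% | any | 0 |
| 5% | 1 | −0.05 |
| 5% | 3 | −0.15 |
| 10% | 2 | −0.20 |
| 10% | 3 | −0.30 |
| 20% | 3 | −0.60 |
| 30% | 4 | −1.20 |

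With 30 per arm, one extra APL-9 subject with a 3-point event moves the difference by 3/30 = 0.10 points. With a strictly predose baseline the shift is 0.

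**Step 5. The last-single-predose reading.** Assume no true change, three readings per later day, and a within-day SD s on the total score. The expected maximum of three normal readings lies 0.846 × s above their mean.
- Single predose reading against later worst of three: 0.42 at s = 0.5 and 0.85 at s = 1.0. Simulation gave +0.42 and +0.84, a false worsening.
- Worst of three against worst of three: simulated drift 0.

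For the respiratory item alone, one PaO2/FiO2 reading against the worst of four gives about 0.25 points (assumed median 150 mm Hg, within-day CV 15%), and about half that at half the CV. Without a treatment effect these drifts are equal in both arms, so they cancel in the Part 2 comparison. They cannot cancel in Part 1, which has no control arm.

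**The case against.** The best defence is that baseline already means predose in these documents. Protocol 11, 12.3 and 12.4 and SAP 6 all say so, and the phrase about worst daily values may only describe how a score is formed. That is a fair reading, and no passage says that baseline SOFA uses the whole of Day 1. A reader might infer that baseline is definitely contaminated; the documents support only an unresolved conflict. The defence does not close the point, because it leads to the single-reading comparison of Step 5.

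A reader might also infer that laboratory items are scored as the worst of three draws on Day 1 against one draw later, giving a built-in improvement. On assumed CVs of 6%, 6% and 10% for platelets, creatinine and bilirubin, that would add about 0.14 points to baseline (0.07 at half those CVs, 0.22 at 1.5 times). But no passage prescribes it. Protocol 11.1.1 uses local laboratory data without limiting it to scheduled draws, so later days may also have several values.

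The strongest inference would be that early drug harm will be presented as efficacy. The documents do not support that:
- Nothing in them shows an excess of post-dose events on APL-9. Protocol 5.2 reports no significant safety findings in healthy volunteers, although protocol 9.1.1 does provide for reactions to the loading dose.
- An adverse event after the first dose would also count as a TEAE under the primary endpoint.
- SOFA is summarised at each assessment, so a raised baseline in one arm would be visible.
- The two required criteria for starting Part 2 do not use SOFA.

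**Conclusion.** The point holds as a conflict between rules. SAP 6.2.2, protocol 11.1.1 and Appendix 1 score baseline SOFA on the dosing day from worst daily values without a predose cut-off. Protocol 11, 12.3 and 12.4 and SAP 6 require a predose baseline. Two programmers could follow the plan and obtain different changes from baseline.

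Under the literal rule the arm difference is biased only if transient Day 1 deterioration differs by arm, and then by f × d. No rate is documented, so the values in Step 4 are a range on assumptions and the true shift may be zero. Under the last-single-predose rule the drift is toward worsening in both arms, about 0.4 to 0.8 points on the assumed within-day SDs. It matters mainly for the within-arm summaries and for Part 1.

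SOFA is a secondary endpoint with descriptive analysis only. No test or sample size depends on it. The plan should be corrected, but the trial's main conclusions do not turn on this.

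**What to change.** State in SAP 6.2.2, protocol 11.1.1 and Appendix 1:

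*Baseline SOFA uses the worst value of each component, including any local laboratory result, recorded in the 24 hours before the first dose. Values after the start of the first infusion are not used for baseline. Post-baseline scores use the worst value of the visit day.*

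Add a CRF instruction to record whether each Day 1 component value is predose. Without it a post-dose blood pressure may be the only Day 1 value kept. When editing Appendix 1, also align its laboratory source: it names the central laboratory for platelets, bilirubin and creatinine, while protocol 11.1.1 and Table 2 name the local one.

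This keeps baseline free of treated hours and gives about one day of observation on each side.

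The cost is wording plus a small CRF-instruction change. Protocol 11 already accepts routine-care procedures as baseline data within the scheduled time frame. The documents do not show whether the current eCRF (version 6.0) captures a 24-hour look-back, so that must be checked. Subjects admitted shortly before dosing will have a shorter look-back, and many will have a single predose laboratory value. Some asymmetry remains for them if later days have several results.
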